5.6.5 Treatment Verification

Weekly orthogonal films or cone beam CT's should be performed to verify patient setup (at least).

5.6.6 Radiation Treatment Breaks

Ideally, treatment breaks, if necessary, should not exceed 5 treatment days at a time and 10 treatment days total. Treatment breaks should be allowed only for resolution of severe acute toxicity and/or for intercurrent illness and not for social or logistical reasons.

5.7 Chemotherapy

In our initial study, LCCC 1120, all patients were started on a regimen of cisplatin $30\text{mg}/\text{m}^2$ given intravenously over 60 minutes weekly during IMRT; 6 total doses for a total of $180\text{ mg}/\text{m}^2$. However, if cisplatin was not tolerated, it was permissible to switch to alternative, acceptable weekly chemotherapy regimens such as cetuximab, carboplatin, or carboplatin/taxol. For the proposed study, cisplatin is the preferred mandated first choice chemotherapy, however alternative weekly regimens are permissible. Typical reasons for a patient not being able to receive cisplatin include renal insufficiency and history of hearing loss. Justification for not using cisplatin must be documented.

Analysis of a prospective national registry, Longitudinal Oncology Registry of Head and Neck Carcinoma (LORHAN), showed that the three most commonly prescribed concurrent (with radiation) regimens (in order) are single agent cisplatin (51%), single-agent cetuximab (21%), and carboplatin plus paclitaxel (7%). Single agent carboplatin was infrequently used (3%) [redacted] et al. Cancer 2011;117:1679–86.). The acceptable weekly chemotherapy regimens that may be used on this study are the following:

- Cisplatin 30 to $40\text{ mg}/\text{m}^2$ (preferred, first choice)
- Cetuximab $250\text{mg}/\text{m}^2$ (preferred, second choice)
- Carboplatin AUC 1.5 and paclitaxel $45\text{ mg}/\text{m}^2$ (preferred, third choice)
- Carboplatin AUC 3 (preferred, fourth choice)

Chemotherapy will be given intravenously weekly during radiotherapy. 6 total doses will be given. It is preferred that the doses be administered on days 1, 8, 15, 22, 29, and 36;

however, this is not mandatory. Patients with the p53 mutation will receive one additional weekly chemotherapy dose. *Chemotherapy will not be given to patients with T0-2 N0-1 disease, < 10 pack years smoking history. For patients with T0-2 N0-1 disease, >10 pack years smoking history, whether or not the patient receives chemotherapy will be at the discretion of the treating physician.*

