1.2 Standard of care CRT for OPSCC

The standard treatment regimen for HPV-associated oropharyngeal or unknown primary squamous cell carcinoma of the head and neck is 70 Gy, 2 Gy per day, 35 fractions, over 7 weeks with 2 to 3 doses of cisplatin 100mg/m². Most institutions perform a PET/CT at 10 to 16 weeks after CRT to assess response. Depending on the clinical response, patients may have to have a biopsy of the primary site and/or a neck dissection after treatment. Typically patients with a negative PET/CT scan are observed (i.e. no surgery). Standard CRT is associated with significant acute toxicity with most patients experiencing grade 3 and 4 acute toxicity during treatment. Furthermore, approximately 20% of patients will have Grade 3-4 long-term morbidity related to their definitive CRT.

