5.0 STUDY PLAN

5.1 Schema

[figure not shown]

Figure 2: Schema

Figure 2: The primary objective of this study is to assess the 2 year PFS of HPV-associated OPSCC after genetic risk based de-intensified CRT. All patients with ≤ 10 pack years smoking history will receive de-intensified CRT. Patients with > 10 pack years smoking history, and select patients with extensive smokeless tobacco history (based on the PI's assessment), will have genetic assessment of their tumors (pre-treatment archival tissue or biopsies), and if p53 is mutated, they will receive an additional 10 Gy for a total radiation dose of 70 Gy (which is the historical, standard) and one additional weekly chemotherapy dose. Those with > 10 pack year smoking history and without the p53 mutation will receive the de-intensified regimen. Circulating free HPV DNA will be assessed pre-treatment, during treatment, and post-treatment at months 3, 6, 12, 18, and 24 (See Section 5.5 for details on blood collection time points).

5.2 Pretreatment Evaluations: All patients will have standard of care evaluation and staging procedures.

5.2.1 Complete history and physical exam including weight and performance status.

5.2.2 Completion of panendoscopy with directed biopsies and bilateral tonsillectomies if the primary is unknown is strongly recommended, but not required.

5.2.3 Completion of the following radiological studies:

at least contrasted neck CT and chest x-ray. Chest CT, PET/CT and/or MRI are optional studies. CT of the neck should have IV contrast unless contraindicated (allergy or adverse reaction or renal issues). PET/CT is satisfactory and can be done instead of or in addition to contrasted neck CT and chest x-ray. Pretreatment ultrasound evaluation with possible FNA is permissible to stage the neck prior to treatment.

5.2.4 Complete dental evaluation is recommended.

5.2.5 Completion of the following laboratory studies: CBC, serum chemistries, liver function tests, and pregnancy test if female.

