5.7.1 Dose Modifications for chemotherapy

Because of the low weekly dosage of chemotherapy, we anticipate few dose modifications secondary to acute toxicities. Dose modifications are allowed and will be directed by the treating medical oncologist according to his/her discretion on an individual patient basis.

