6.2 Reporting

Patients will be receiving radiation, chemotherapy, and surgical treatments within the accepted standard of care. We expect patients to experience the known toxicities that are associated with these standard treatments, but only at a lower rate and severity than patients treated with accepted radiation and chemotherapy dosing. Since treatments modalities are the same (radiation and chemotherapy), but doses of radiation and chemotherapy are reduced through this deintensification protocol, no adverse events will be attributable to the trial treatment. In the RTOG 0129 study, based on the same deintensification treatment, the overall rate of grade 3 or 4 acute toxic events was approximately 80% and the late grade 3 or 4 toxic events was approximately 25% of those seen in control patients treated with accepted radiation and chemotherapy doses. Because patients on this trial receive de-intensified chemotherapy and radiation by reducing the total dose of radiation to 60 Gy and administering no chemotherapy or Cisplatin 30mg/m² weekly the acute and late toxicities can only be decreased in trial patients compared to historical norms.

This de-escalation trial decreases radiation and chemotherapy doses compared to accepted dosing for head and neck cancer; therefore, adverse events will not be reported since there is no chance that adverse events are trial related.

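### Section 6.2 waives adverse-event reporting on a description of treatment (60 Gy, and cisplatin 30 mg/m² or none) that the treatment sections do not match

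*Combined protocol and SAP*

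**What the plan says.** Section 6.2 gives the dose rationale. On radiation it speaks of "reducing the total dose of radiation to 60 Gy". On the drug side, and on what it takes to follow for toxicity, it says "administering no chemotherapy or Cisplatin 30mg/m² weekly the acute and late toxicities can only be decreased in trial patients". From this it draws the rule that "adverse events will not be reported since there is no chance that adverse events are trial related". It also has a separate ground, that the modalities used are standard of care with known toxicities. The amendment log records that Amendment 15 added a justification to this section, so this is current text.

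The treatment sections of the same version read differently:

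- Section 5.7 lists as its first regimen "Cisplatin 30 to $40\text{ mg}/\text{m}^2$ (preferred, first choice", given weekly for 6 doses. Cetuximab, carboplatin with paclitaxel, and carboplatin alone follow as alternatives.
- Section 5.7 adds: "Patients with the p53 mutation will receive one additional weekly chemotherapy dose".
- Section 5.1 says of patients found to be p53-mutated: "they will receive an additional 10 Gy for a total radiation dose of 70 Gy (which is the historical, standard". Section 5.6 repeats the 70 Gy total for those with more than 10 pack years.
- Section 5.7.1 says: "Dose modifications are allowed and will be directed by the treating medical oncologist according to his/her discretion".

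The comparator is in Section 1.2: "70 Gy, 2 Gy per day, 35 fractions, over 7 weeks with 2 to 3 doses of cisplatin 100mg/m²". Section 1.3 states the standard more narrowly, as 70 Gy with three cycles at 100 mg/m².

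Toxicity is still to be observed. Section 6.1 adopts CTCAE version 4.0, the Section 10.2 table keeps a row for physician CTCAE grading, and Section 7.3 keeps periodic reports to the DSMC.

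**The concern.** A rule that removes adverse-event reporting needs a premise that is true of everyone it covers. Section 6.2 claims certainty: toxicity can go only one way, and trial-related events are impossible. It derives this from one radiation dose and one cisplatin dose. If some patients may receive more cisplatin than stated, a different drug, or the full standard radiation dose, the claim fails for them.

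What is at stake is the use of safety data the trial still plans to collect. Physicians grade toxicity and the DSMC receives reports, yet 6.2 says events go unreported. Taken literally, the rule could leave the DSMC without the toxicity results it would need to check the very assumption in 6.2.

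**Working it through.** **Inputs**

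- Weekly cisplatin: 30 mg/m² in 6.2; 30 to 40 mg/m² in 5.7.
- Number of doses: 6, or 7 with a p53 mutation (5.7).
- Standard cisplatin: 2 to 3 × 100 mg/m² (1.2); 3 × 100 mg/m² (1.3).
- Radiation: 60 Gy in 6.2; 60 + 10 Gy for p53-mutated patients with more than 10 pack years (5.1, 5.6); standard 70 Gy (1.2).

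**Formula.** Cumulative dose = number of doses × dose per administration, assuming every planned dose is given unmodified.

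**The plan's own figure.** Section 5.7 gives 180 mg/m² for the earlier study LCCC 1120. 6 × 30 = 180, so it reproduces.

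**Standard.** 2 × 100 = 200 and 3 × 100 = 300 under 1.2; 300 only under 1.3.

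**Permitted totals**

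| Planned doses | At 30 mg/m² | At 40 mg/m² | Against 200 | Against 300 |
|---|---|---|---|---|
| 6 | 180 | 240 | 180/200 = 0.90 to 240/200 = 1.20 | 180/300 = 0.60 to 240/300 = 0.80 |
| 7 (p53-mutated) | 210 | 280 | 210/200 = 1.05 to 280/200 = 1.40 | 210/300 = 0.70 to 280/300 = 0.93 |

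**Where the overlap with 1.2 begins.** With 6 doses, 200/6 = 33.3 mg/m² weekly. With 5 doses delivered, 200/5 = 40, the top of the range. With 4 doses it cannot occur, since 4 × 40 = 160. With 7 doses, 200/7 = 28.6, below the permitted minimum, so every permitted dose gives a total above 200.

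**Radiation.** 60 + 10 = 70 Gy, and 70 − 70 = 0 Gy below the standard for p53-mutated patients with more than 10 pack years.

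**The description in 6.2 against the permitted treatment**

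- Radiation of 60 Gy: true of patients not assigned the boost; not true of those who are.
- No chemotherapy or cisplatin 30 mg/m²: both are permitted, but so are cisplatin above 30 and up to 40 mg/m², and three non-cisplatin regimens that this description omits.
- Toxicity can only fall: this does not follow for patients planned for 70 Gy and 7 doses, and the documents give no toxicity comparison that would establish it for the other permitted regimens.

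**The case against.** The strongest reply has four parts.

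*The overlap says nothing direct about toxicity.* This stands. The documents do not equate cumulative weekly dose with 100 mg/m² boluses. The overlap also depends on the two-dose end of 1.2: against the 300 mg/m² in 1.3, every permitted total is lower. A reader might infer that the trial regimen is as toxic as standard treatment, or more so. The documents do not support that, and radiation is still lower for everyone planned for 60 Gy.

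*30 mg/m² is a permitted dose.* This also stands. Section 6.2 is incomplete; it does not cite a forbidden dose.

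*The standard-of-care ground is independent, and the 70 Gy is disclosed elsewhere.* Section 1.1 says plainly that p53-mutated smokers receive standard doses, and 5.7 cites registry data showing that the alternative agents are used in practice. Correcting the dose alone would therefore leave part of the rationale in place. But that ground supports expecting familiar toxicities. It does not support saying that trial-related events are impossible. It also means that changing 30 to 30–40 is not enough: the no-reporting sentence has to be replaced as well.

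*Safety oversight already exists.* True, and it limits the point. A reader might infer that toxicity is no longer observed at all; Sections 6.1, 7.3 and 10.2 show otherwise. The remaining difficulty is that 6.2 conflicts with them.

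**Conclusion.** The point holds in a limited form. The dose rationale in 6.2 does not describe the permitted treatment, and its two absolute conclusions are wrong as written.

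Planned cisplatin is 180 to 240 mg/m² rather than 180 only, and 210 to 280 mg/m² with 70 Gy for p53-mutated patients with more than 10 pack years who are given cisplatin. Section 5.7 leaves chemotherapy to the physician in T0-2 N0-1 disease above 10 pack years, so not all of them need receive it. All totals assume full planned dosing.

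The documents do not say how many patients received more than 30 mg/m² or had a p53 mutation. The share dosed above 30 could be anything from none to all of those given cisplatin.

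A reader might go further and infer that the mixed chemotherapy undermines the 2-year PFS result. That is not established here. The sample size and binomial rule do not depend on 6.2, and mixed regimens were already allowed in LCCC 1120 and 1413. A table of chemotherapy delivered, or narrower wording of the PFS conclusion, would be optional reporting detail.

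**What to change.** In Section 6.2:

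1. Replace the single cisplatin dose with the regimens in 5.7, including the 30 to 40 mg/m² range. State that patients with more than 10 pack years and a p53 mutation receive 70 Gy and a seventh weekly dose.
2. Delete the statement that toxicity can only go down and the statement that trial-related events are impossible. The standard-of-care ground may stay, as a reason to expect known toxicities.
3. Replace the no-reporting sentence with a rule such as: physician CTCAE assessments scheduled in Section 10.2 are summarised, separately for patients treated to 60 Gy and to 70 Gy, in the DSMC reports required by Section 7.3.

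The cost is a wording amendment and a small amount of tabulation. It needs no new visits, assessments or committee, and the primary analysis is unchanged.

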tumor and either have \leq 10 pack years of tobacco smoking and any N stage or >10 pack years of tobacco smoking and N0-N2a nodal stage.

O'Sullivan et al. conducted a large retrospective study of 899 OPSCCs patients treated at the Princess Margaret Hospital in Toronto, Canada³². HPV status was ascertained in 505 (56%): 382 HPV positive and 123 HPV negative. All patients were treated with radiation alone or CRT from 2001 to 2009, with a median follow-up of 3.9 years. Recursive portioning analysis segregated HPV-positive patients into low (T1-3 N0-N2c) and high (T4 or N3) distant metastasis risk: 93% vs. 76% respectively. Furthermore, smoking > 10 pack years reduced overall survival but did not impact recurrence free survival (local, regional, and distant recurrences) in HPV-positive patients. This suggests that other associated tobacco-related disease may be the reason for decreased survival in HPV-positive smokers vs. HPV-positive non-smokers. Also, the recurrence free survival was excellent (>90%) in low-risk HPV-positive patients with T1-2, N0-1 disease treated with RT alone vs. CRT. Thus the addition of chemotherapy to radiation in this very favorable low-stage subset may not be necessary.

An unanswered question is whether we can safely de-intensify in patients with HPV-associated OPSCC who have significant smoking histories (> 10 pack years). The proposed study will help to answer this question.

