2.0 STUDY OBJECTIVES

2.1 Primary Objective:

To evaluate whether genomic based risk-stratification can be used in deciding whether to de-intensify in patients with HPV-associated OPSCC with > 10 pack years smoking history. Hypothesis: Patients with HPV-associated OPSCC, > 10 pack years smoking history, and non-mutated p53 will have similar 2 year PFS as patients with < 10 pack years smoking history.

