7.2 Data Analysis Plan

The main hypothesis test will be performed as described above. Subgroup analyses to compare PFS between patients with ≤ 10 pack years vs patients with > 10 pack years (but with no p53 mutation) smoking history will be conducted using log-rank test. Additionally, a Kaplan-Meier curve will be estimated for PFS, local control, regional control, local-regional control, distant metastasis free survival and overall survival. Circulating free HPV DNA before, during, and after CRT will be compared, using the paired t-test or McNemar's test as appropriate. As an exploratory analysis, joint modeling of longitudinal cfHPV-DNA and time-to-progression will be conducted to examine the association between time-varying cfHPV-DNA and disease progression. We will also perform exploratory analyses of the other genetic alterations that are assessed by the TruSight Tumor Panel® and fluorescent in-situ hybridization studies.

In addition to the above, other exploratory analyses utilizing study-related data may be performed. These analyses will be consistent with the overarching aims of the study.

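### In T0-2 N0-1 disease the chemotherapy rule differs by smoking group, so the unstratified log-rank comparison in 7.2 mixes smoking history with chemotherapy use

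*Combined protocol and SAP*

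**What the plan says.** The primary objective (2.1) carries the hypothesis that patients with more than 10 pack years and "non-mutated p53 will have similar 2 year PFS as patients with < 10 pack years smoking history". The only planned analysis that sets these groups against each other is in 7.2: "Subgroup analyses to compare PFS between patients with ≤ 10 pack years vs patients with > 10 pack years (but with no p53 mutation", ending "smoking history will be conducted using log-rank test". No stratification factor, covariate, margin or power is given for it.

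The general chemotherapy rule in 5.7 is the same for everyone: "Chemotherapy will be given intravenously weekly during radiotherapy. 6 total doses will be given", with one extra dose for patients with the p53 mutation. For the lowest stages 5.7 then splits by smoking. In the lighter group, "Chemotherapy will not be given to patients with T0-2 N0-1 disease, < 10 pack years smoking history". In the heavier group at the same stage, "whether or not the patient receives chemotherapy will be at the discretion of the treating physician", and no criteria are given.

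The schema text in 5.1 says of the heavier smokers: "Those with > 10 pack year smoking history and without the p53 mutation will receive the de-intensified regimen". It also says that all patients with 10 pack years or fewer receive de-intensified CRT.

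**The concern.** The comparison in 7.2 is meant to show whether heavier smokers without a p53 mutation do as well as light smokers on the same reduced regimen. In T0-2 N0-1 disease the regimens may not be the same. Both groups follow the 60 Gy plan, but light smokers get radiotherapy alone by rule, while some or all of the heavier smokers may also get chemotherapy. The treatment difference lies along the variable being compared.

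If chemotherapy improves PFS at this stage, a real deficit in heavier smokers could be partly offset and the curves read as similar. That matters more because the hypothesis is similarity while the tool is a test for difference with no stated margin, so a non-significant result is easily taken as support. Adjusting for chemotherapy within T0-2 N0-1 does not solve it, since by rule no light smoker there receives any.

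**Working it through.** **1. The plan's own figures.** None is given for the smoking comparison. The current figures in 7.1 belong to the single-arm test (n = 225, reject at 23 or more failures):

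- P(X ≥ 23 | 225, 0.07) = 0.0446; stated 0.045.
- P(X ≥ 23 | 225, 0.14) = 0.9628; stated 0.96.

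Both reproduce. Smoking group does not enter this test as a comparison.

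**2. Protocol treatment in the two groups compared** (5.1, 5.6, 5.7). Eligibility in 4.1.2 is T0-3, N0 to N2c, so everything outside T0-2 N0-1 is T3 or N2.

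| Stage group | Light smokers | >10 pack years, no p53 mutation |
|---|---|---|
| T0-2 N0-1 | 60 Gy, no chemotherapy | 60 Gy, chemotherapy at physician's discretion |
| T3 or N2 | 60 Gy, six weekly doses | 60 Gy, six weekly doses |

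Only the first row differs by smoking.

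**3. Effect in a treated patient (assumed values).** Let S be the 2-year PFS on radiotherapy alone and HR the chemotherapy hazard ratio. PFS with chemotherapy is S^HR. With S = 0.86:

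- HR 0.9: 0.873
- HR 0.8: 0.886
- HR 0.7: 0.900
- HR 0.6: 0.913

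Against 0.93, the first closes (0.873 − 0.86)/0.07 = 19% of the gap and the last (0.9135 − 0.86)/0.07 = 76%. This applies only to treated T0-2 N0-1 patients.

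**4. Effect on the all-patient comparison.** Let s be the T0-2 N0-1 share (taken as equal in both groups) and u the chemotherapy uptake among heavier smokers of that stage. Neither is in the documents. The shift in favour of the heavier group is s × u × (S^HR − S).

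| S | Smallest: s = 0.10, u = 0.50, HR 0.9 | Largest: s = 0.40, u = 1.00, HR 0.6 |
|---|---|---|
| 0.86 | 0.05 × 1.31 = 0.07 points | 0.40 × 5.35 = 2.14 points |
| 0.90 | 0.05 × 0.95 = 0.05 points | 0.40 × 3.87 = 1.55 points |
| 0.93 | 0.05 × 0.68 = 0.03 points | 0.40 × 2.74 = 1.10 points |

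With HR = 1 the shift is 0 in every row. So it is about 0.1 to 2 points from the 86% starting value, and less from higher ones.

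**5. Sensitivity of the log-rank test.** The failure rates in 7.1 imply 225 × 0.07 ≈ 16 to 225 × 0.14 ≈ 32 events. Assume 20-40% of patients (a) are in the heavier group, two-sided alpha 0.05 and a true HR of 2. Schoenfeld power is Φ(√[events × a(1 − a)] × ln 2 − 1.96):

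- 16 events, a = 0.2: Φ(1.109 − 1.96) ≈ 0.20
- 32 events, a = 0.4: Φ(1.921 − 1.96) ≈ 0.48

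On these assumptions the comparison would often miss even a doubled hazard without any bias, so there is little room for a systematic shift.

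**The case against.** The strongest objection is that the effect may be negligible. Section 1.4 reports recurrence-free survival above 90% in low-risk T1-2 N0-1 patients treated with radiotherapy alone versus CRT, says smoking over 10 pack years did not affect recurrence-free survival in HPV-positive patients, and concludes: "Thus the addition of chemotherapy to radiation in this very favorable low-stage subset may not be necessary". That stands as a limit on size. It does not remove the point, because no planned analysis would show whether it holds here.

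A reader might infer several stronger things that the documents do not support:

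- **That a large part of a 7-point deficit would be hidden.** The 19-76% in step 3 covers only treated patients in one stage group. The 0.86 behind it is the whole-trial alternative in 7.1, not a figure for this stage.
- **That the bias certainly favours the hypothesis, or that chemotherapy is given according to prognosis.** The first requires that chemotherapy helps at this stage. For the second, 5.7 gives no criteria, and physician selection could push either way.
- **That the contrast changed over the accrual period.** The amendment log dates the discretion to Amendment 6 but does not state the rule before it.
- **That the trial's pass/fail test is compromised.** It is a single-arm test on the whole group, and 7.2 labels the smoking comparison a subgroup analysis.
- **That T3 or N2 should replace the all-patient comparison.** This would lose patients and narrow the question in 2.1. Nor is that stratum fully uniform: agent, dose modification and switching are discretionary (5.7 to 5.7.2). Under 5.1, selected smokeless-tobacco users with mutated p53 receive 70 Gy and an extra dose. Those with 10 pack years or fewer would sit in the light-smoking group.

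**Conclusion.** The point holds in a limited form. In T0-2 N0-1 disease the chemotherapy rule depends on smoking history, and 7.2 pools that stage group into an unstratified log-rank test. Similar PFS in that test could not be attributed to p53 selection alone.

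The size cannot be established from the documents. The range of about 0.1 to 2 percentage points rests on assumed stage share, uptake, hazard ratio and starting PFS, and it falls to zero if chemotherapy has no effect at this stage. If chemotherapy helps, its own effect leans towards finding similarity; the net direction after physician selection is unknown. The whole-group binomial test stands apart from this. The issue justifies an analysis change, not a challenge to the design.

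**What to change.** In 7.2:

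- Stratify the log-rank test by T0-2 N0-1 versus T3 or N2. This guards against a difference in stage mix and makes the two strata visible, although the T0-2 N0-1 stratum still contributes a mixed contrast.
- Report the T3 or N2 stratum, where 5.7 does not split the rule by smoking, as a pre-specified key sensitivity analysis.
- Tabulate chemotherapy received by smoking group and stage group, and state that within T0-2 N0-1 the smoking and chemotherapy effects cannot be separated.

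Reconcile the pack-year wording. Sections 2.1 and 5.7 describe the lighter group as below 10, while 5.1 and 7.2 include exactly 10; as written, 5.7 assigns no low-stage rule to a patient at exactly 10. The statement in 5.1 that all patients with 10 pack years or fewer receive de-intensified CRT must also be reconciled with the no-chemotherapy rule in 5.7.

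The cost is a few lines of analysis wording and limited precision in the stratum-specific result. Stage and pack years are needed for eligibility and triage. The documents do not list data fields, so the sponsor should confirm that chemotherapy receipt is captured. No change to treatment is proposed.
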